## **6.2           IMPORTANT PROTOCOL DEVIATIONS**

A protocol deviation (PD) is important if it affects the rights or safety of the study patients, or if it can potentially influence the primary outcome measurements in a non-negligible way.

Important Protocol Deviations (IPDs) are stored in the DV domain template (Excel spreadsheet).

If the data show other IPDs, this table will be supplemented accordingly at Medical Quality Review Meetings (MQRMs) or Report Planning Meetings (RPMs) or through team review of the manual PD log. The final list of IPDs will be confirmed before Databaselock (DBL). No per protocol set is defined for this phase I study, but patients with an IPD will be identified and reported in the Clinical Trial Report (CTR).

## **6.3           SUBJECT SETS ANALYSED**

The following subject sets will be defined.

- **Screened Set (ScS):** includes all patients who have signed the informed consent form and will be used for patient disposition.

- **Treated Set (TS):** includes all patients who received at least one infusion of BI 905681. The TS is used for both efficacy and safety analyses, and for summary of demographics, baseline characteristics, disease history, and concomitant therapies.
- **MTD Evaluation Set (MTDS):** includes all patients in the TS who were not replaced for the MTD determination. The MTD Evaluation Set is used for the primary analyses of DLTs and MTD determination. The list of replaced patients will be provided by the Clinical trial leader before DBL and documented in the decision log (2).
- **PK Analysis Set (PKS):** The PK set includes all subjects in the TS who provide at least one observation for at least one PK endpoint without important protocol violations relevant to the evaluation of PK. The PKS is used for all pharmacokinetic analyses

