3.3.4.1 Withdrawal from trial treatment

An individual patient is to be withdrawn from trial treatment if:

- The patient wants to withdraw from trial treatment, without the need to justify the decision.
- Has radiological (or clinical) documentation of progressive disease on the current treatment.
- The patient needs to take concomitant drugs that interfere with the investigational product or other trial medication.
- The patient can no longer be treated with trial medication for other medical reasons (such as surgery, AEs, other diseases, or pregnancy).
- The patient has repeatedly shown to be non-compliant with important trial procedures and, in the opinion of both the investigator and sponsor representative, is not willing or able to adhere to the trial requirements in the future.

Given the patient's agreement, the patient will undergo the procedures for early treatment discontinuation and follow up as outlined in the [Flow Chart](#) (FC) and [Section 6.2.3](#).

For all patients the reason for withdrawal from trial treatment (e.g. AEs) must be recorded in the CRF. These data will be included in the trial database and reported. Patients who withdraw from treatment prior to disease progression should be encouraged to return for full EOT and follow-up assessments as outlined in the [Flow Chart](#). In particular, a follow-up visit should be performed wherever possible to ensure all adverse events are adequately followed up.

During the MTD evaluation period, patients withdrawn for a reason other than having a DLT or patients who miss more than one visit will be replaced after discussion between the sponsor and the Investigator if the information that needed to be collected during that visit is not available and makes the patient non-evaluatable for the PK analyses or safety parameters (including evaluation for DLTs).

Patients who come off trial due to a DLT will not be replaced.

If a patient should become pregnant during the trial, the treatment with BI 905681 must immediately be stopped. The patient will be followed up until delivery or termination of pregnancy (see [Section 5.2.6.2](#) for information on pregnancy forms). The data of the patient will be collected and reported in the eCRF until the last patient's last visit and any events occurring thereafter will be reported in the BI drug safety database as described in [Section 5.2.6](#).

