7.3.1 Primary endpoint analyses

[figure not shown]
In order to identify the MTD of the trial, the number of patients with DLTs at each dose level during the MTD evaluation period (first three weeks for Schedule A and the first 4 weeks for Schedule B) must be presented. Patients who discontinue during the first treatment course for reasons other than a DLT will be excluded from the determination of the MTD.

In addition, the number of patients with DLTs that occurred during the entire treatment period will be summarised at each dose level. The BLRM will be rerun to re-evaluate the MTD and RP2D together with all relevant data collected during the study.

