## **4. CHANGES IN THE PLANNED ANALYSIS OF THE STUDY**

Due to enrollment issues, the trial will be terminated early without determination of the maximum tolerated dose (MTD)/optimal biologic dose (OBD) as per protocol. Only schedule A has been investigated in the trial. The early termination does not have an impact on the planned endpoints.

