## **7.4 PRIMARY ENDPOINT(S)**

### **7.4.1 Primary analysis of the primary endpoint(s)**

In order to identify the MTD of the trial, the number of patients at each dose level that had DLT during the MTD evaluation period (first three weeks for Schedule A) will be presented, excluding patients who discontinue during the first treatment cycle for reasons other than a DLT.

The BLRM as described in Section 7.1 of the CTP will be analyzed using the number of patients at each dose that had DLTs during the MTD evaluation period among the patients in the MTD set. The prior defined in Table 7.1: 1 of the CTP will be used for the analysis. The resulting posterior distribution of the DLT rates of the doses tested during the trial will be summarized using their mean, SD, 2.5% quantile, median, and 97.5% quantile. Additionally, the posterior probabilities of the DLT rate lying in the intervals [0, 0.16) (underdosing), [0.16, 0.33) (target dosing), and [0.33, 1] (overdosing) will be computed and listed for each dose. The posterior probabilities of underdosing, target dosing, and overdosing of the tested dose levels will additionally be visualized in a bar diagram that further displays which of the dose levels satisfy the EWOC criterion.

In addition, the number of patients with DLTs that occurred during the entire treatment period will be summarized at each dose level.

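### SAP 6.3 defines the MTD Evaluation Set by replacement, so read literally an unreplaced first-cycle drop-out without a DLT is left out of the DLT table but counted in the BLRM, contrary to Protocol 7.3.1

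*SAP*

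**What the plan says.** **Protocol.** Section 7.3 restricts MTD determination to MTD-evaluable patients. Section 7.3.1 is specific: "Patients who discontinue during the first treatment course for reasons other than a DLT will be excluded from the determination of the MTD". It does not mention replacement. Replacement is dealt with in section 3.3.4.1. Patients withdrawn in the MTD evaluation period for a reason other than a DLT "will be replaced after discussion between the sponsor and the Investigator", on condition that the missing information makes them non-evaluable for PK or safety, including DLTs.

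**SAP.** Section 6.3 says that the MTD Evaluation Set (MTDS) "includes all patients in the TS who were not replaced for the MTD determination", and that "The MTD Evaluation Set is used for the primary analyses of DLTs and MTD determination". The list of replaced patients comes from the clinical trial leader before database lock. Section 7.4.1 then describes two outputs:
- The DLT table by dose, "excluding patients who discontinue during the first treatment cycle for reasons other than a DLT".
- The BLRM, which uses the number of patients at each dose that "had DLTs during the MTD evaluation period among the patients in the MTD set". The exclusion is not repeated here. The output includes a bar diagram "that further displays which of the dose levels satisfy the EWOC criterion".

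SAP 4 reports that "Due to enrollment issues, the trial will be terminated early without determination of the maximum tolerated dose" (or OBD) and declares no change to the population for the DLT analysis.

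**The concern.** Not being replaced is not the same as being evaluable for DLTs. Replacement depends on a discussion and on what information is missing, whereas the Protocol 7.3.1 exclusion depends only on when and why the patient stopped. The two rules select different patients whenever someone stops in cycle 1 without a DLT and is not replaced.

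Such a patient is out under Protocol 7.3.1 and out of the DLT table. A programmer who derives the MTDS from the replacement list would nevertheless keep the patient in the BLRM. With no recorded DLT, the patient adds one to the denominator and nothing to the numerator. The table and the model for the same primary endpoint would then have different denominators, and the posterior overdose probabilities would be lower than under the protocol's rule. SAP 7.8 bases some safety displays on the MTDS too, so their denominators would follow.

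**Working it through.** **1. Who is in which analysis (patient with a non-DLT discontinuation in cycle 1)**

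| Rule | Replaced | Not replaced |
|---|---|---|
| Protocol 7.3.1, MTD determination | out | out |
| SAP 7.4.1, DLT table | out | out |
| SAP 6.3 with 7.4.1, BLRM | out | **in, as DLT-free** |

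Only the last cell conflicts.

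**2. Model and inputs.** Protocol 7.1: logit(π_d) = log α + β·log(d/4.5), with 4.5 taken on the q3w dose scale. The prior is the three-component mixture of Protocol Table 7.1: 1, which SAP 7.4.1 retains. The posterior is proportional to prior × Π π_d^r (1 − π_d)^(n − r), computed by grid integration. P(overdose) is the posterior probability that π_d ≥ 0.33, and EWOC requires it to be below 0.25. A drop-out counted as DLT-free multiplies the likelihood by one extra factor (1 − π_d).

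**3. Reproducing the plan's figures.**
- Prior P(overdose) at 1, 2.5, 4.5, 6.5 and 8.5: 0.074, 0.117, 0.178, 0.247, 0.299. Protocol Table 7.1: 2 gives 0.072, 0.114, 0.177, 0.244, 0.295.
- Protocol scenario 6 (0/3, 0/3, 1/6 at 4.5, 2/6 at 6.5): 0.241 at 6.5, against 0.246 stated.
- All ten scenarios in Table 10.3: 1 agree within 0.010. Counts are taken as 3 patients per cohort entry, which the text of Appendix 10.3 supports.

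**4. Effect at the administered doses.** The doses 1.0, 2.5, 5.0, 7.0 and 8.5 are from SAP Table 6.1: 1. Assumed: 3 evaluable patients per dose, plus one drop-out counted as DLT-free at 8.5. The documents give no actual counts.

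| DLTs | P(overdose at 8.5), drop-out excluded | Drop-out counted | EWOC at 8.5 |
|---|---|---|---|
| none | 0.006 (0/3) | 0.003 (0/4) | met in both |
| one at 8.5 | 0.077 (1/3) | 0.051 (1/4) | met in both |
| two at 8.5 | 0.336 (2/3) | 0.240 (2/4) | fail becomes pass |
| one at 7.0, one at 8.5 | 0.262 (1/3 at each) | 0.187 (1/4 at 8.5) | fail becomes pass |

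In the last row a drop-out at 7.0 (0.215) or at 5.0 (0.243) also crosses the limit.

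**5. How often status changes.** DLTs were placed in every way over 5.0, 7.0 and 8.5, one DLT-free patient was added at any dose, and EWOC was checked at all five doses.

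| Patients per dose, lowest to highest | No DLT | One DLT | Two DLTs |
|---|---|---|---|
| 3/3/3/3/3 | 0 of 1 | 0 of 3 | 2 of 6 |
| 2/2/3/3/3 | 0 of 1 | 0 of 3 | 2 of 6 |
| 3/3/3/3/6, 3/3/3/6/3 or 3/3/3/6/6 | 0 of 1 | 0 of 3 | 0 of 6 |

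**6. Cohorts of six can cross with more DLTs.**
- Scenario 6, if one of the six at 6.5 were such a drop-out: 0.241 with 2/6, but 0.318 with 2/5.
- 0/3 at the three lowest doses, 1/3 at 7.0 and 2/6 at 8.5: 0.294; with 2/7 at 8.5, 0.225.

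Both examples have three DLTs in total.

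**The case against.** The strongest reply is that one population is plainly intended. SAP 3 says that the SAP rests on Protocol section 7, SAP 4 declares no change to this population, and SAP 6.3 assigns the MTDS to both the DLT analyses and the MTD determination. Protocol 3.3.4.1 links replacement to non-evaluability, so being replaced works as the trial's label for non-evaluable. The intention is accepted, but the definition does not deliver it. The BLRM paragraph names its own population, and that population is defined without the exclusion.

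A second reply limits the consequence, and it stands. A reader might infer that keeping such a patient always biases the DLT rate downward. The documents do not support that. Schedule A has one infusion per 21-day cycle, AEs are collected until the patient's end of trial, and the follow-up visit falls 42 to 49 days after the last dose. Someone who stops treatment on day 15, say, can still be observed for the whole DLT window, and DLT-free is then a true observation. Bias requires that the patient was not replaced and that the window was incompletely observed. Protocol 7.3.1 would exclude the patient in either case, so the conflict in wording remains.

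A reader might also infer that a patient replaced only for PK reasons drops out of the MTDS. The qualifier in SAP 6.3, which ties replacement to MTD determination, points the other way.

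**Conclusion.** The point holds as a minor conflict of definitions. Read literally, the MTDS departs from Protocol 7.3.1 and gives the DLT table and the BLRM different denominators whenever a non-DLT first-cycle drop-out was not replaced. Downward bias follows only if that patient's 21-day window was not fully observed.

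In the cases examined, with 3 patients at each administered dose, EWOC status does not change with no DLT or one DLT. It can change with two or more DLTs, for example 0.336 to 0.240 with two at 8.5. It would be wrong to conclude that only very small cohorts are affected: scenario 6 has six patients at 6.5 and still crosses. All of these figures rest on assumed counts.

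Two stronger readings are not supported. Early termination for enrolment reasons makes an unreplaced drop-out conceivable, but nothing shows that there was one. Nor does an MTD or an escalation decision hang on this analysis, because the trial ends without an MTD. Within the primary analysis, what can change is the reported posterior and the EWOC display.

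**What to change.** In SAP 6.3, before database lock:
- Define the MTDS by the rule of Protocol 7.3 and 7.3.1: treated patients, excluding those who discontinued in the first cycle for reasons other than a DLT or were otherwise not evaluable for DLTs, whether or not they were replaced.
- State that this one set is used for both the DLT table and the BLRM in SAP 7.4.1.
- List the excluded patients with reasons.

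The cost is a change of SAP wording. The model may lose a few patients and the posterior may be slightly wider. If there is no unreplaced non-DLT drop-out and no other non-evaluable patient in the set, the results do not change.

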## **6.5 POOLING OF CENTRES**

This section is not applicable because center/country is not included in the statistical model.

## **6.6 HANDLING OF MISSING DATA AND OUTLIERS**

Every effort should be made to collect complete data at each visit for each patient. Missing baseline laboratory values will be imputed by the respective values from the screening visit. Potential outliers will be reported and analyzed as observed. If not specified otherwise, missing data will not be imputed and remain missing. No other imputations will be performed on missing data although every effort will be made to obtain complete information on AEs, with particular emphasis on potential DLTs.

Missing or incomplete AE dates will be handled according to the Boehringer Ingelheim (BI) guideline (3). Missing data and outliers of PK data will be handled according to the BI standards (4).

## **6.7 BASELINE, TIME WINDOWS AND CALCULATED VISITS**

### **Visit labels**

Study days and visits will be labelled according to the CTP's flow chart. The visit schedule with accompanying details can also be found in the flow charts in the CTP.

### **Baseline definition**

Unless otherwise specified, baseline is defined as the time point closest to and prior to the first administration of study treatment. Note that for some study procedures (e.g. body weight, vital signs, laboratory tests) baseline may be the measurement made on the same day the study treatment was started. In such cases these measurements will be assumed to have been taken according to the protocol, i.e. prior to the first administration of study treatment. But for some measurements, the examination time may also need to be considered, in instances where

time is recorded in addition to date. If not available, then the values reported at the screening visit will be considered.

For laboratory parameters for which not only the examination date but also the sampling time was recorded, examination time should be taken into consideration when defining baseline. That is a laboratory measurement on the same date as the first administration of study treatment is considered as baseline if and only if the examination time of this laboratory measurement is before the first administration of study treatment.

## **7. PLANNED ANALYSIS**

For End-Of-Text (EoT) tables, the set of summary statistics includes: N / Mean / standard deviation [STD] / Min / Median / Max.

Tabulations of frequencies for categorical data will include all possible categories and will display the number of observations in a category as well as the percentage (%) relative to the respective treatment group (unless otherwise specified, all patients in the respective patient set whether they have non-missing values or not).

Percentages will be rounded to one decimal place. The category missing will be displayed only if there are actually missing values.

If needed, conversion from days to weeks, months and years will be as follows:

- Weeks=Days/7
- Months=(Days\*12)/365.25
- Years=Days/365.25

### **7.1 DEMOGRAPHIC AND OTHER BASELINE CHARACTERISTICS**

Only descriptive statistics are planned for this section of the report.

### **7.2 CONCOMITANT DISEASES AND MEDICATION**

Only descriptive statistics are planned for this section of the report.

Concomitant therapies (CTh) will be coded according to World Health Organisation Drug Dictionary (WHO DD). They will be classified according to the Anatomical, Therapeutic, Chemical (ATC) classification system. The third ATC level will be used to categorise CThs by therapy type. In situations where a medical product may be used for more than one equally important indication, there are often several classification alternatives. As appropriate, patients receiving CThs with more than one possible ATC level-three category will be counted more than once; footnotes will clarify this possible double counting in tables.

Summaries will be presented for previous and concomitant medications started at baseline and for concomitant therapies started after first administration of the trial medication.

### **7.3 TREATMENT COMPLIANCE**

Only descriptive statistics are planned for this section of the report.

Compliance with trial medication will be based on the drug infusion/administered eCRF data and calculated as amount of drug infused/administered divided by the amount of drug to be infused/administered expressed as a percentage, see calculations below.

“Per Cycle” compliance to trial medication will be calculated as follows:

$$\frac{(\text{Amount of drug infused/administered at Cycle n})}{(\text{Amount of drug planned to be infused/administered at Cycle n})} \times 100.$$

Overall compliance to trial medication will be calculated as mean of the “per cycle” compliance.

The compliance will be based on the total volume infused in mL (eCRF data) compared to total volume prepared (eCRF data).

## **7.4 PRIMARY ENDPOINT(S)**

### **7.4.1 Primary analysis of the primary endpoint(s)**

In order to identify the MTD of the trial, the number of patients at each dose level that had DLT during the MTD evaluation period (first three weeks for Schedule A) will be presented, excluding patients who discontinue during the first treatment cycle for reasons other than a DLT.

The BLRM as described in Section 7.1 of the CTP will be analyzed using the number of patients at each dose that had DLTs during the MTD evaluation period among the patients in the MTD set. The prior defined in Table 7.1: 1 of the CTP will be used for the analysis. The resulting posterior distribution of the DLT rates of the doses tested during the trial will be summarized using their mean, SD, 2.5% quantile, median, and 97.5% quantile. Additionally, the posterior probabilities of the DLT rate lying in the intervals [0, 0.16) (underdosing), [0.16, 0.33) (target dosing), and [0.33, 1] (overdosing) will be computed and listed for each dose. The posterior probabilities of underdosing, target dosing, and overdosing of the tested dose levels will additionally be visualized in a bar diagram that further displays which of the dose levels satisfy the EWOC criterion.

In addition, the number of patients with DLTs that occurred during the entire treatment period will be summarized at each dose level.

## **7.5 SECONDARY ENDPOINT(S)**

[figure not shown]
### **7.5.1 Key secondary endpoint(s)**

[figure not shown]
Not applicable.

### **7.5.2 (Other) Secondary endpoint(s)**

Descriptive statistics will be presented for Cmax and AUC0-tz. The analysis of standard PK parameters and pharmacodynamic analyses will be performed as outlined in Section 7.3.5 of the CTP, if applicable and feasible.

## **7.7 EXTENT OF EXPOSURE**

Treatment exposure will be primarily summarized by the total on-treatment time and has been defined in [Section 5.4](#) of this TSAP.

## **7.8 SAFETY ANALYSIS**

All safety analyses will be performed on the treated set. In addition, some displays will be based on the MTD evaluation set and the MTD evaluation period.

### **7.8.1 Adverse Events**

Adverse events will be coded using the Medical Dictionary for Drug Regulatory Activities (MedDRA). Standard BI summary tables and listings will be produced. All adverse events with an onset between start of treatment and end of the residual effect period (REP), a period of 42 days after the last dose of trial medication, will be assigned to the on-treatment period for evaluation.

All treated patients will be included in the safety analysis. In general, safety analyses will be descriptive in nature and will be based on BI standards. No hypothesis testing is planned.

Statistical analysis and reporting of adverse events will concentrate on treatment-emergent adverse events, i.e. all adverse events occurring between start of treatment and end of the residual effect period. Adverse events that start before first drug intake and deteriorate under treatment will also be considered as ‘treatment-emergent.’

The analyses of adverse events (AE) will be descriptive in nature. All analyses of AEs will be based on the number of patients with AEs and not on the number of AEs. Frequency of patients with AEs will be tabulated by treatment dose, highest CTCAE grade, system organ class (SoC) and preferred term after coding according to the current version of MedDRA at the database lock. In addition, AEs will be tabulated by preferred terms only. The SoC will be sorted alphabetically. In tables displaying AEs by preferred terms, this will be sorted by descending frequency of AEs in the “Total” BI 905681 group.

Summary tables and listings of AEs, SAEs, related AEs, related SAEs, AEs of special interest, AEs leading to dose reduction, AEs leading to treatment discontinuation and AEs leading to deaths will be provided.

For the analysis of DLTs with regard to the primary endpoint see [Section 7.4.1](#).

